### **8.2.9 Abnormal laboratory test results**

Abnormal laboratory test results will be recorded in the CRF. Any abnormal laboratory test results that meet SAE criteria should be reported as SAE in addition to recorded as an AE in the CRF.

On the AE page of the CRF, any abnormal clinically significant laboratory test results caused by the treatment should be recorded as a single diagnostic result, i.e., these results meet one or more of the following:

- Occurrence of clinical complications.
- Leading to a change in the study medication (e.g., dose change, dosing suspension, or permanent discontinuation).
- Concomitant therapy changes (e.g., additions, interruptions, discontinuations, or any other changes of the concomitant medications, treatments, or medications) are required.

**This applies to** any laboratory safety and efficacy results that are obtained from the examinations performed after administration of the first dose of study drug and are/are not specified in any protocol. These results are outside of the laboratory reference range and meet the criteria for clinical significance.

**This does not apply to** any abnormal laboratory test results that are outside the laboratory reference range but do not meet the criteria for clinical significance (they will be analyzed and reported as laboratory abnormalities); AEs that are specifically excluded by the protocol; or results from AEs reported or being reported.

If there are medically significant unexplained laboratory abnormalities, the examinations should be repeated, and followed up until they return to the normal range and/or they are found to be adequately explained. If they have been clearly explained, they should be recorded on the CRF.

### **8.3 Pregnancy**

If a female patient becomes pregnant during the study period, the study drug must be discontinued as directed and the Investigator shall be notified immediately. The Investigator shall report the pregnancy results to the Sponsor, the pharmaceutical regulatory authority, and the Ethics Committee through the Clinical Trial Pregnancy Report Form within 24 hours. The Investigator should give medical advices and discuss with the patient about the the risks of continuing the pregnancy and possible effects on the fetus. The patient should be monitored until the end of the pregnancy, and if the baby is born alive, the baby should be followed up. Pregnancy that occurs within 90 days of completion of study dosing should also be reported to the Investigator.

If the spouse of a male patient participating in the study becomes pregnant or becomes pregnant within 90 days of the end of the study medication, an informed consent form that is signed by the pregnant spouse must be obtained from the Pregnant Spouse Data Release Form, and the pregnant spouse should be followed up, and the pregnancy outcome should be reported to the Investigator and the Sponsor. The spouse should be consulted to discuss the risks of continuing the pregnancy and possible adverse effects on the fetus. The patient should be monitored continuously until the end of the pregnancy. If the baby is born alive, the baby should also be followed up.

### **9 Independent Review Committee (IRC)**

An Independent Review Committee (IRC) consists of two radiologists with the certification for review and assessment of radiographic findings and one certified oncologist. They will review patient radiographic images (CT, MRI, PET/CT, bone scan) independently in accordance with RECIST 1.1 to confirm postoperative local recurrence or metastasis.

The review by an independent review committee does not determine eligibility for enrolment or the treatment of patients. The Investigator makes all treatment decisions based on local assessment results. The

analysis of OS and DFS is based on the Investigator's assessment results.

The imaging examinations (CT, MRI, PET/CT, bone scan) of the patients enrolled in this study during the baseline period and periodic postoperative follow-up visits need to be collected according to the imaging acquisition guidelines of this study, and transferred to the personnel of the Independent Review Committee.

2.1 Primary Objective

To evaluate the efficacy of adjuvant icotinib, in terms of 3-year disease-free survival (DFS), for patients with completely resected stage IB non-small cell lung cancer (NSCLC).

2.2 Secondary Objectives

To evaluate the efficacy of adjuvant icotinib, in terms of DFS, for patients with completely resected stage IB NSCLC, as compared with observation.

To evaluate the efficacy of adjuvant icotinib, in terms of central nervous system (CNS)-related DFS, for patients with completely resected stage IB NSCLC, as compared with observation.

To evaluate the efficacy of adjuvant icotinib, in terms of overall survival (OS), for patients with completely resected stage IB NSCLC, as compared with observation.

To assess the safety and tolerability of adjuvant 12-month icotinib for patients with completely resected stage IB NSCLC, as compared with observation.

2.3 Exploratory Objectives

To evaluate the efficacy of adjuvant icotinib for patients with completely resected stage IB NSCLC based on the AJCC 7th and 8th edition of staging.

To evaluate the efficacy of adjuvant icotinib for patients with completely resected stage IB NSCLC based on sensitive EGFR mutation and all EGFR mutations (including atypical EGFR mutations).

3 Study Design and Methods

3.1 Study Design

This is a phase II, open-label, randomized controlled study to evaluate the efficacy and safety of adjuvant icotinib for patients with completely resected stage IB NSCLC without adjuvant chemotherapy.

The decision of not receiving adjuvant chemotherapy will be according to physician and patient choices.

Eligible patients will be randomized in a 1:1 ratio to receive adjuvant therapy with icotinib (125 mg, three times daily) or to undergo observation. Treatment with icotinib will be given for up to 12 months or until discontinuation criteria are met. Therapy will be continued until disease progression or intolerable toxicity occurred. The first dose of study treatment should be taken no later than 7 days of randomization.

3.2 Randomization

Randomization will be performed by the study staff of the GASTO through a computer-generated sequence with a minimization method that balanced sex (male vs. female) and ECOG PS (0 vs. 1) for random assignment. Randomization will be performed just before the initiation of study administration. Eligible patients will be randomly assigned in a 1:1 ratio to either receive oral icotinib or undergo observation.

3.3 Blinding

Not applicable. This is an open-label study. All investigators, study personnel, and patients will be not masked to patient distribution.

4 Study Endpoints

4.1 Efficacy Endpoints

4.1.1 Primary Efficacy Endpoint

The primary endpoint are 3-year DFS, which is defined as the proportion of patients who were disease free at 3 years.

4.1.2 Secondary Efficacy Endpoints

The secondary endpoints included DFS (time from random assignment to documented disease recurrence or death, whichever occurred first), central nervous system (CNS)-related DFS (time from randomization to CNS recurrence or death, whichever occurred first), overall survival (OS, time from random assignment to death from any cause).

4.2 Safety Endpoints

All patients who receive at least 1 dose of study treatment will be evaluated for safety and tolerability. Safety and tolerability will be evaluated at every visit. All adverse events (AEs) will be classified according to the National Cancer Institute's Common Terminology Criteria for Adverse Events (NCI-CTCAE) version 4.0. Proportion of patients with AEs will be recorded for patients in the icotinib group. Grade 3 or greater AEs will be recorded. The number and percentage of subjects reporting serious adverse events (SAEs) will be summarized.

AEs will be managed according to the AE management protocol.

5 Sample Size

On the basis of the CALGB 9633 trial [1], we projected a 3-year DFS of 60% for patients with stage IB NSCLC. The study is designed to determine whether adjuvant icotinib would result in a 17% absolute improvement (from 60% to 77%) in 3-year DFS, with 80% power at a two-sided α of 0.1. This improvement corresponded to an HR of 0.5. Assuming an accrual time of 2 years, a follow-up time of 3 years, and an anticipated dropout rate of 5%, a total of 128 patients would be required to be randomly assigned. This sample size is sufficient to power this study at 80% with a two-sided type I error rate of 10%.

6 Patient characteristics

Patient demographics will be summarized. The patient demographics will include the following:

Age

Sex

Baseline ECOG PS

Smoking status

Disease characteristics will be summarized. Disease characteristics will include the following:

Pathological diagnosis

Primary tumor size

Tumor stage

Tumor grade

Tumor location

EGFR mutational status

Tumor stage will be derived based on pathological results.

7 Treatment Compliance

Treatment compliance of icotinib will be summarized. Compliance will be calculated as the ratio of total dose taken to the total assigned dose (minus any dose adjustments and doses omitted/withheld). The treatment time (days and months) will be calculated.

8 Interim Analysis

Not applicable. No interim analyses were planned.

9 Subgroup Analysis

To investigate the interaction between treatment effect and the subpopulation, subgroup analyses will be conducted in an exploratory manner with respect to the following factors: sex (male vs. female) and EGFR mutation (exon 19 deletion vs. exon 21 L858R).

10 Statistical Considerations

The Intention-To-Treat Set (ITT) will include all randomized subjects. ITT will be used for the analysis of DFS and OS.

All analyses for efficacy are based on ITT population.

The Safety Analysis Set will include all subjects who received at least 1 dose of study drug and have a safety record after drug administration.

Descriptive statistics will be defined for continuous variables as number (n), median, mean, minimum and maximum, and as frequency and percentage for categorical variables.

The Kaplan-Meier method [2] will be used to estimate the point estimates of 3-year DFS for each group. The difference in 3-year DFS between groups will be compared by the Z test. The median DFS and OS will be estimated by the Kaplan-Meier method and the differences between median DFS and OS will be compared by the log-rank test.

Hazard ratios and their 95% confidence intervals for treatment effects are estimated using Cox proportional hazards models [3].

Unless otherwise specified, all statistical analyses will be performed using two-sided tests with a significance level of 0.05. All statistical analyses will be performed using SPSS and R.

11 Variables

Month=365/12 days.

Year=365 days.

Time since diagnosis to randomization = date of randomization – date of initial diagnosis) +1.

The duration of treatment was calculated as the (last dose date – first dose date) + 1.

Duration in study (days) = last day of known to be alive – date of randomization + 1

Follow-up time (days for DFS) = date of recurrence (patient who had recurrence) or date of last follow-up – date of randomization + 1.

Follow-up time (days for OS) = date of death (patient who died) or date of last follow-up – date of randomization + 1.

12 Missing data

No imputations will be made for missing data. Patients who does not have relapse or death will be censored at last follow-up.

13 References

3. Cox D. Regression models and life-tables. *J Royal Stat Soc Ser B*. 1972; 34: 187-220.

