Duration of study	It is planned to enroll 128 patients based on about 6 patients enrolled each month; and the time for enrollment is about 24 months; the minimum survival follow-up period is 3 years, and the total study period will last about 60 months.
Study Drug Dosage/Route of Administration/Regimen	
Group A (icotinib group): Patients start to receive oral icotinib 125 mg, tid, for 12 months after R0 resection of NSCLC, or discontinue treatment due to tumor recurrence or intolerance.
 
Group B (control group) Patients are followed up after R0 resection of NSCLC.

Study Procedure	
After patients have signed the informed consent forms (ICFs) and meet the inclusion and exclusion criteria, they will be randomly assigned to the icotinib group and the control group.
 
Patients need to be evaluated. The patients receive the visits once every 3 months during the dosing period, and once every 6 months for the survival follow-up until the disease recurrence or death.
 
The Investigator shall contact the patient, the patient's family, or the patient's current physician by phone at least once every 3 months after recurrence, to collect the long-term follow-up information on survival. Any patient who withdraws from study treatment for reasons other than recurrence (except patient's withdrawal of informed consent, loss to follow-up, death) should continue to receive the objective tumor evaluation every 6 months to collect the information on recurrence.

Safety	All patients who have received at least one treatment with study drug will be included as the effective population for safety analysis. The patient's physical examination results, vital signs, adverse events, and abnormal laboratory test results will be summarized. Adverse events should be reported and graded according to the NCI Common Terminology Criteria for Adverse Events (CTCAE) version 4.0.
Statistical Analysis	The sample size is 128 for the following considerations: based on previous studies, the 3-year DFS for stage IB NSCLC is about 60%, the hazard ratio (HR) is 0.5, the test power ( $1 - \beta$ ) is 80%, and the test level ( $\alpha$ ) is two-sided 10%; enrollment period of 24 months, and total study period of 60 months.

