### **3.3 Duration of study**

It is planned to enroll 128 patients based on about 6 patients enrolled each month; and the time for

enrollment is about 24 months; the minimum survival follow-up period is 3 years, and the total study period will last about 60 months.

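### The stated 80% power does not belong to the stated primary test: with 128 patients, the Z test of 3-year DFS at two-sided 0.10 has about 65–70%

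*SAP*

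**What the plan says.** - **Endpoint.** SAP section 4.1.1 makes 3-year DFS primary, "defined as the proportion of patients who were disease free at 3 years". Protocol section 3.6.1 defines it the same way. DFS as a time-to-event variable is secondary.
- **Primary test.** SAP section 10 estimates 3-year DFS by Kaplan-Meier in each arm, then: "The difference in 3-year DFS between groups will be compared by the Z test". The log-rank test is assigned to DFS and OS.
- **Sample size.** SAP section 5 targets a "17% absolute improvement (from 60% to 77%) in 3-year DFS", "with 80% power at a two-sided α of 0.1", equates this with a hazard ratio of 0.5, and assumes 2 years of accrual, 3 years of follow-up and 5% dropout. It arrives at 128 randomised patients and states: "This sample size is sufficient to power this study at 80% with a two-sided type I error rate of 10" per cent.
- **Synopsis.** The protocol synopsis gives the same 128 patients, 80% power and two-sided 10%, from the premise that "the 3-year DFS for stage IB NSCLC is about 60%, the hazard ratio (HR) is 0.5". It mentions no dropout.
- **Follow-up.** Protocol section 3.3: "the minimum survival follow-up period is 3 years".
- **General significance level.** SAP section 10: "Unless otherwise specified, all statistical analyses will be performed using two-sided tests with a significance level of 0.05".

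Neither document names the test or formula that produced 128.

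**The concern.** SAP section 5 expresses both the effect and the power on the scale of the primary endpoint, so a reader will take 80% as the power of the 3-year DFS comparison. A comparison of two proportions at a fixed time does not use the timing of events or the events after 3 years, so it usually needs more patients than a log-rank test for the same hazard ratio. A sample size taken from a hazard-ratio calculation would therefore overstate the power of the landmark test.

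Two things are at stake. A non-significant primary result would be judged against a 20% miss rate when the true rate is appreciably higher. In addition, the level for the primary test is not stated where that test is defined, so a p-value between 0.05 and 0.10 could be called either way after the data are seen.

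**Working it through.** **Inputs.** Control 3-year DFS 60%; target 77%, or 0.6^0.5 = 77.46% if the hazard ratio is exactly 0.5; 1:1 allocation, so 64 per arm; 5% dropout, so 0.95 × 64 = 60.8 per arm; two-sided alpha 0.10 (critical value 1.645); 2 years of accrual and at least 3 years of follow-up. All are from SAP sections 3.1 and 5, the protocol synopsis and protocol section 3.3.

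**1. Can the plan's 80% be reproduced?** Only approximately, and only with a different test or sidedness.

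*Log-rank (Schoenfeld), assuming exponential DFS and uniform accrual:*
- Control hazard = −ln(0.6)/3 = 0.1703 per year; icotinib hazard is half of that.
- Event probabilities over the study: 0.491 and 0.288, mean 0.3896.
- Events for 80% power: 4 × (1.645 + 0.842)² / (ln 0.5)² = 51.5. N = 51.5/0.3896 ≈ 132, or 139 after 5% dropout.
- With 128 patients: 128 × 0.3896 = 49.9 events; power = Φ(½ × √49.9 × ln 2 − 1.645) = Φ(2.448 − 1.645) = **78.9%**.
- With 5% dropout (121.6 patients, 47.4 events): **77.1%**.

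*Z test at one-sided 0.10, 64 per arm:* 78.9–79.5% for 77% and 80.6–81.3% for 77.46% without dropout. With 5% removed: 77.3–78.0% and 79.1–79.8%.

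**2. Power of the stated test at the stated alpha.** With no loss before 3 years, the Greenwood variance of the Kaplan-Meier estimate equals the binomial variance.

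- Unpooled: SE = √[(0.6 × 0.4 + 0.77 × 0.23)/64] = 0.0807; power = Φ(0.17/0.0807 − 1.645) = **67.8%**.
- Pooled null variance: mean proportion 0.685, null SE = √(2 × 0.685 × 0.315/64) = 0.0821; power = Φ[(0.17 − 1.645 × 0.0821)/0.0807] = **66.7%**.

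The same formulas give:

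| Per arm | Comparison | Two-sided 0.10 (pooled / unpooled) | Two-sided 0.05 (pooled / unpooled) |
|---|---|---|---|
| 64 | 60% vs 77% | 66.7% / 67.8% | 54.5% / 55.8% |
| 64 | 60% vs 77.46% | 69.0% / 70.0% | 56.9% / 58.3% |
| 60.8 | 60% vs 77% | 64.8% / 65.8% | 52.3% / 53.7% |
| 60.8 | 60% vs 77.46% | 67.0% / 68.1% | 54.7% / 56.1% |

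**3. Simulation of the Kaplan-Meier Z test** (Greenwood variance, 40,000 trials per scenario; exponential DFS, uniform accrual, data cut at month 60). Without dropout: 68.2% (77%) and 70.3% (77.46%). With 5% censored at a uniform time within 3 years: 66.8% and 69.5%. Simulated type I error at nominal 0.10 was 0.104.

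**4. What 80% would need with this test.**
- Unpooled: n per arm = (1.645 + 0.842)² × (0.24 + 0.1771)/0.17² = 89.2, so 90 per arm, 180 in total. For 77.46%: 84.1, so 85 per arm, 170 in total.
- Pooled: 92 per arm (184) and 87 per arm (174).
- Allowing for 5% dropout, from 170/0.95 to 184/0.95: about 179 to 194 randomised.

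**5. What 64 per arm can detect with 80% power.** From 60% to 79.7% (unpooled) or 80.0% (pooled), a difference of 19.7–20.0 points and a hazard ratio of about 0.44.

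**The case against.** - **The 128 may come from a hazard-ratio calculation.** The synopsis inputs (hazard ratio, accrual, total duration, no dropout) are those of a log-rank design, which gives 78.9%, close to 80%. This may explain the number, but no section says so. Log-rank is not the primary test, and with the SAP's own 5% dropout that figure falls to 77.1%.
- **The slip may be in the sidedness.** A one-sided 0.10 Z test with hazard ratio 0.5 and 5% dropout gives 79.1–79.8%. That is about as close, but both documents say two-sided. The origin of 128 cannot be settled from the documents, and this uncertainty stands.
- **The low end of the range deletes dropouts.** The SAP censors them at last follow-up, so they contribute until then. Simulations that handle them this way give about 67–71% across scenarios with and without dropout. This is fair as to the lower bound, but it moves the answer by only about 2 points against a gap of 10–15.
- **The alpha is already specified.** SAP section 5 ties 0.10 to the 3-year DFS target, so the general 0.05 rule arguably does not reach it. That is the more natural reading. However, section 5 gives 0.10 as a design input and section 10, which defines the test, has no exception, so a sentence is still needed.
- **This is a phase II trial and only wording changes.** True: neither the sample size nor the conduct is affected. The stated power is nonetheless wrong for the stated test.

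**Conclusion.** The concern holds. At two-sided 0.10 with 128 patients, the primary Z test has about 65–70% power, some 10–15 points below the stated 80%: strictly, about 65–68% for 60% versus 77% and 67–70% for 60% versus 77.46%. The chance of missing the targeted improvement is about 30–35% instead of 20%. If the general 0.05 level were applied, power would be about 52–58% and the miss rate about 42–48%.

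The figures without dropout (66.7–70.0%) rest only on the plan's own rates, sample size and minimum follow-up. The dropout figures depend on how a 5% loss is treated, which the SAP does not define. The log-rank and simulation figures also assume exponential DFS and uniform accrual. Type I error at the stated 0.10 is not affected.

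**What to change.** - **SAP section 5 and protocol synopsis:** restate the power of the primary Z test as about 65–70% at two-sided 0.10 with 128 patients, separating 77% from 77.46%. Name the test, the variance formula and the dropout handling behind the figure. If the sponsor can recover the calculation that gave 128, record it there and label it with the test it applies to.
- **SAP section 10:** state that the primary comparison of 3-year DFS uses two-sided 0.10, as in section 5, and that the 0.05 level applies to the other analyses.
- **Keep** the 128 patients, the endpoint and the Z test. Do not switch the primary test to log-rank merely to recover the 80%.

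The cost is wording in three places. The only downside is a less favourable stated power.

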### **3.6.2 Safety indicators**

All patients who have received at least one study drug treatment will serve as a valid population for safety analysis. Physical examination findings, vital signs, adverse events and abnormal laboratory test results of the patients will be summarized. Adverse events should be reported and graded according to the NCI Common Terminology Criteria for Adverse Events (CTCAE) Version 4.0.

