### **7.2 Analysis types**

#### Intention-to-treat population

Statistical analysis will be performed in the intention-to-treat (ITT) population. ITT population is defined as all enrolled patients.

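### The SAP makes safety compared with observation a secondary objective, but its safety set admits only dosed patients, so no observation patient can enter it

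*SAP*

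**What the plan says.** The objective, in SAP Section 2.2, is: "To assess the safety and tolerability of adjuvant 12-month icotinib for patients with completely resected stage IB NSCLC, as compared with observation".

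The safety population is stated five times, each time with a dose or exposure condition:

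- SAP Section 10: "The Safety Analysis Set will include all subjects who received at least 1 dose of study drug and have a safety record after drug administration".
- SAP Section 4.2: "All patients who receive at least 1 dose of study treatment will be evaluated for safety and tolerability".
- Protocol Synopsis, Safety row: "All patients who have received at least one treatment with study drug will be included as the effective population for safety analysis".
- Protocol Section 3.6.2: "All patients who have received at least one study drug treatment will serve as a valid population for safety analysis".
- Protocol Section 7.2, safety analysis population: the same rule, with results to be shown by treatment received.

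On reporting, SAP Section 4.2 adds: "Proportion of patients with AEs will be recorded for patients in the icotinib group". Its sentences on grade 3 or higher AEs and on serious AEs name no arm.

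Protocol Section 3.5.1 gives the control group follow-up only, with no study drug. The protocol lists safety and tolerability among its secondary endpoints (Synopsis and Section 3.6) without naming a comparator.

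**The concern.** An objective that compares two arms needs an analysis set containing both. Here the objective names observation as the comparator, and the rule for entering the safety set excludes anyone who was never dosed.

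If the analysis follows the text, the safety tables have one arm. Some AEs will occur after lung resection with or without icotinib. Without a control column, the planned tables cannot separate that background from events seen on drug. If the analyst adds the observation arm later to meet the objective, then the population, the starting point and the recording period will be chosen after open-label data have been seen.

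**Working it through.** The documents give no size for the safety set, so there is no planned figure to reproduce. The check is a head count followed by a reading of every clause that might admit the controls.

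**Head count**

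- Total randomized: 128 (SAP Section 5). Allocation: 1:1 (SAP Sections 3.1 and 3.2).
- Observation arm: 128 × 1/2 = 64. Minimization may move this by a few patients, hence about 64.
- Observation patients with at least one dose, if treated as assigned: 0 (Protocol Section 3.5.1).
- Safety set as written: at most 64 icotinib patients + 0 observation patients = 64.
- Safety set if undosed observation patients were admitted: up to 64 + 64 = 128.

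**Clauses that might admit the controls**

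1. *Study treatment in SAP Section 4.2.* This term could be stretched to include observation. The condition, however, is a dose of it, and observation has none. SAP Section 10 says study drug and also asks for a safety record dated after administration.
2. *Presentation by treatment received (Protocol Sections 7.2 and 7.3).* This grouping applies within a population already limited to dosed patients. Everyone in it received icotinib, so the grouping has a single level.
3. *The intention-to-treat (ITT) population.* Protocol Section 7.2 opens with a general statement that analysis will be by ITT and adds: "ITT population is defined as all enrolled patients". It then defines a separate population for safety. The SAP is narrower: "ITT will be used for the analysis of DFS and OS", followed by a sentence assigning all efficacy analyses to ITT. Neither document assigns safety to ITT.
4. *The grade 3 or higher and serious AE sentences in SAP Section 4.2.* They carry no arm restriction, but they stand under that section's dose-based population sentence.

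None of the four brings an undosed patient into the set.

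**Data collection, checked separately**

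- Protocol Section 3.7.2 has AEs documented at each visit, with no limit by arm.
- Footnote E to the study flow chart collects AEs from consent.
- Protocol Section 8.2.5 requires serious AEs to be reported whatever treatment the patient is on.

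These rules point towards control-arm data being recorded. The flow chart did not survive text extraction well enough to show which arm's columns carry the AE marks, so it is not used either way.

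**The case against.** The strongest reply is that this is one loosely worded phrase. All four secondary objectives in SAP Section 2.2 close with the same words, so the phrase may have been carried over to the safety objective by habit. The protocol never frames safety as a comparison, the five population statements agree with one another, and no between-arm safety test is planned. On that reading the trial always meant to describe safety on icotinib only, and deleting the phrase settles the matter.

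Much of this stands. The comparative wording is in the SAP alone, and a two-arm safety analysis is not the only way to restore consistency. It does not remove the contradiction: the SAP states an objective and defines a set that cannot serve it, and the documents do not show which was intended.

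Two stronger readings are tempting and should be resisted:

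- *That control-arm AEs are not collected, so a comparison is impossible.* The visit, consent and serious AE rules cited above point the other way. Control data could be tabulated, but no planned analysis set admits them.
- *That AE recording is shorter by a known amount in icotinib patients who stop early.* Protocol Section 8.2.7 does end AE recording by reference to the last dose, which controls do not have. But visit-based recording under Section 3.7.2 is limited by neither arm nor dosing, and the documents give no stopping times. No figure for such a difference can be supported.

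**Conclusion.** The point holds as an inconsistency between a stated secondary objective and the analysis set meant to serve it. All five safety-population statements exclude undosed patients, so 0 of about 64 observation patients can enter and the planned safety analysis has one arm. The count assumes an approximately even split and no control given icotinib in error.

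No effect on AE rates is estimated, because the documents give no control-arm rates. The primary analysis of 3-year disease-free survival is not touched. The matter should be corrected before analysis, but it does not threaten the trial's main conclusion.

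**What to change.** **Preferred: keep the comparison.** Amend SAP Sections 10 and 4.2, and to match, the Protocol Synopsis and Sections 3.6.2 and 7.2:

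- Define the safety set as icotinib patients with at least one dose plus patients randomized to observation who received no icotinib, grouped by treatment received. An observation patient given icotinib in error is then shown under icotinib.
- Apply the safety-record condition alike in both arms: after first dose for icotinib, after randomization for observation.
- Replace the icotinib-only sentence in SAP Section 4.2. Tabulate AEs, grade 3 or higher AEs and serious AEs by arm, descriptively, over one stated period common to both arms.
- Keep drug-relatedness tables for icotinib only.

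The cost is text in two SAP sections and three places in the protocol. The protocol change needs Ethics Committee approval under Protocol Section 5.5. No new visits are needed, since the existing ones already document AEs. There are two limitations to state with the results: AE reporting in an open-label trial may be less complete in controls, and with about 64 per arm the comparison will be imprecise for uncommon events.

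**Fallback: drop the comparison.** Delete the comparative phrase from the safety objective in SAP Section 2.2 and state that safety is descriptive for icotinib only. This is one SAP edit with no change to the safety set, at the price of giving up the comparison with observation.
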